6.5 Monitoring of trial

The last DSMB meeting occurred on 23 January 2020 and the interim monitoring is now complete. The following describes the original monitoring plan for the trial.

HVTN 702 will be formally monitored for four types of events that may lead to a modification or termination of the trial. The first three components of the plan monitor vaccine efficacy for potential-harm, non-efficacy/efficacy futility, and high-efficacy (Table 6-4). The potential harm monitoring uses exact binomial tests to compare the rates of vaccine and placebo infections. The non-efficacy and high-efficacy monitoring are based on VE measured by the ratio of cumulative incidences (vaccine vs placebo), with point estimates calculated by the transformation of the Nelson-Aalen estimator and Wald-based confidence intervals.

This section provides an overview of the principles underlying the monitoring approach. The details of the approach and its operating characteristics will be described in the SAP. Of note, all 4 types of monitoring apply to pooled data across both sexes. Sex-specific infection numbers, incidence estimates, and VE estimates will be provided to the DSMB, but no formal sex-specific monitoring guideline will be used due to the smaller number of infections, and hence lower precision of estimation, within each sex.

Table 6-4 Sequential monitoring of vaccine efficacy. CI = confidence interval, LL = lower limit, UL= upper limit. VE(0-24) is vaccine efficacy from enrollment through Month 24; VE(6.5-36) is vaccine efficacy from Month 6.5 (Week 26) through Month 24; VE(0-36) is vaccine efficacy from enrollment through Month 36.

Monitoring Type	Hypotheses	Statistical Method	Timing of Interim Analyses
Potential Harm	H0: VE(0-24) ≥ 0% vs. H1: VE(0-24) < 0%	Exact binomial test 5% overall Type I error rate	After every infection starting at the 12 th until the first non-efficacy analysis
Non- Efficacy	H0: VE(0-24) ≥ 40% vs. H1: VE(0-24) < 40% and H0: VE(6.5-24) ≥ 40% vs. H1: VE(6.5-24) < 40%	For both VE(0-24) and VE(6.5- 24), LLs of 95% CIs < 0% and ULs of 95% CIs < 40%	Starting at 59 infections and occurring every 50 infections thereafter, until the end of Stage 1 (up to 7 analyses)
High Efficacy	H0: VE(0-36) ≤ 70% vs. H1: VE(0-36) > 70%	95% CI for VE(0-36) lies above 70%	Synchronized with non-efficacy monitoring in Stage 1 contingent on at least 100 participants having reached the Month 36 visit to evaluate VE(0-36), and one analysis halfway through Stage 2

6.5.1 Monitoring for harm

The unblinded statisticians (Section 6.5.8) will "continuously monitor" the trial (ie, examine the data after each confirmed MITT infection endpoint) for early evidence of a potential elevated rate of HIV-1 infection in the vaccine group compared to the placebo group [ie, VE(0-24) < 0%]. The potential harm monitoring follows a classic sequential monitoring framework and utilizes a (nearly) constant boundary on the p-value scale that is determined via controlling the overall type I error rate across tests at 0.05. Such analyses start at the 12th infection (pooled over the vaccine regimen and placebo) and will occur subsequently at each additional infection until the first interim analysis for non-efficacy, after which the non-efficacy analyses serve the function of stopping for potential harm. If the prespecified stopping boundary is reached, then the unblinded statisticians will immediately inform the DSMB. In addition, the DSMB chair will be updated on the accruing unblinded HIV-1 infection data after each confirmed MITT infection. This monitoring guideline is chosen to allow stopping for prudence as early as possible, maximizing participant safety.

Note that the potential-harm monitoring is not intended to reliably establish harm [ie, VE(0-24) < 0%], as a vaccine regimen could meet the boundary and the reported 95% confidence interval for VE(0-24) would include 0%. Rather, the objective is to apply extra caution and prudence for a prevention trial that enrolls healthy volunteers.

6.5.2 Monitoring for non-efficacy/efficacy futility

The DSMB will monitor the vaccine for non-efficacy/efficacy futility, defined as evidence that it is highly unlikely that the vaccine has a beneficial effect on acquisition of VE(0-24) of 40% or more. Such analyses will start at 59 infections, which is chosen as the first infection total when a 95% confidence interval about

an estimated VE(0-24) = 0% (based on a Cox proportional hazards model) would lie below 40%. Analyses will take place in increments of 50 infections until the end of Stage 1. The criterion for non-efficacy is that, for both VE(0-24) and VE(6.5-24), the lower limit of the 95% confidence interval lies below 0% and the upper limit lies below 40%. By checking both VE(0-24) and VE(6.5-24) confidence intervals, the monitoring plan is designed to protect against stopping prematurely based on ramping vaccine efficacy over the intercurrent period of 0-6 months. For each parameter, VE is estimated 2 ways. First, defining VE as 1 minus the ratio of cumulative HIV incidence estimates, vaccine vs. placebo, VE is estimated by the transformation of the Nelson-Aalen estimator for the cumulative hazard function. Second, VE measured by 1 minus the hazard ratio (HR) for HIV infection is estimated using Cox proportional hazards regression. Confidence intervals for both VE estimates must satisfy the non-efficacy criterion for both VE(0-24) and VE(6.5-24). The rationale for using both cumulative-incidencebased and proportional-hazards-based VE estimates is that: 1) the former better protects against concluding non-efficacy due to ramping vaccine efficacy but the latter is more stable at early interim analyses; and 2) proportional-hazards-based VE estimates are used to determine when to start the interim monitoring and are universally used in vaccine efficacy studies. When there are sufficient numbers of infections in each sex at birth to ensure stable confidence interval estimates, sexstratified VE estimates based on both approaches will be provided as described in Section 6.9.5.1.

6.5.3 Monitoring for high efficacy

Monitoring of high efficacy allows early detection of a highly protective vaccine if there is evidence that vaccine efficacy from enrollment through 36 months [VE(0-36)] is above 70%. Analyses will be harmonized with those for non-efficacy monitoring, with the exception that the high efficacy analyses will only start once at least 100 participants have reached the terminal Month 36 visit. This condition ensures that sufficient follow-up has accumulated to estimate VE(0-36). If Stage 2 occurs, there will be one final high efficacy interim analysis that occurs 6 months into Stage 2. The criterion for high efficacy is that the 95% confidence interval for VE(0-36) lies above 70%. Here again, VE is estimated using a ratio of cumulative incidences and using Cox proportional hazards regression, and the high efficacy criterion must be satisfied by both estimators. Note that, whereas the monitoring for potential-harm and non-efficacy restricts to infections diagnosed between Months 0 and 24, the monitoring for high-efficacy would only be warranted under some evidence for durability of vaccine efficacy.

6.5.4 Definition of the end of Stage 1 and criterion for continuing to Stage 2

Whereas the timing of interim analyses is event-driven, the total number of Stage 1 infections is not fixed. The end of Stage 1 is when the last enrolled participant reaches the Month 24 visit. Ensuring all participants are followed to Month 24 maximizes power and precision for assessing VE(0-24).

Early stopping of the vaccine regimen will be recommended if one of the potential harm or non-efficacy boundaries is met at a prespecified analysis time, in which case a decision will be made regarding whether to follow participants to Month 24 (Stage 2 will not occur). If the high-efficacy boundary is met at a planned interim analysis, the vaccine regimen will be declared highly efficacious and placebo recipients may be offered the vaccine even while follow-up continues through Stage 1 (or Stage 2, if applicable). If none of the stopping boundaries are reached by the end of Stage 1, vaccine efficacy from enrollment through Month 24 [VE(0-24)] is evaluated at the end of Stage 1. VE is defined as 1-cumulative incidence ratio (vaccine vs. placebo) and is estimated by the transformation of the Nelson-Aalen estimator for the cumulative hazard function. If the lower bound of the 95% confidence interval for VE(0-24) is > 0% at the end of Stage 1 (equivalently, the 1-sided p-value for testing H0: $VE(0-24) \le 0\%$ is above 0.025), trial participants will continue blinded follow-up through Stage 2. On the other hand, if at the Stage 1 efficacy analysis the lower bound of the 95% confidence interval for VE(0-24) $\leq 0\%$, Stage 2 will not occur even if none of the stopping boundaries were reached by the end of Stage 1. This corresponds to continuing to Stage 2 if, at the end of Stage 1, the estimated VE(0-24) is approximately 19-21% or greater; the range of VE values is due to uncertainty in the total number of Stage 1 infections.

6.5.5 Monitoring for operational futility

The DSMB monitors the trial for operational futility, defined as overly slow progress toward full enrollment or sufficient numbers of MITT infections to support the primary analysis, and by other measures of underperformance. Approximately semi-annual DSMB meetings will be held for monitoring operational futility during the closed session, synchronized with interim analyses of vaccine efficacy. At the time of each semi-annual DSMB meeting, the HVTN 702 Oversight Group (OG) will receive the components of the operational futility analysis that are based on blinded data (pooled across treatment arms), as described below.

The first component of the operational futility monitoring plan includes projections of the time until enrollment completes. Under design assumptions, enrollment is expected to take 20 months. The projection of this time, including an assessment of its probability distribution, will be presented to the DSMB, and compared with the pre-trial assumptions.

The second component of the operational futility monitoring plan includes projections of the probability distribution of the treatment-arm-pooled infection total, and the arm-specific infection totals, over 0-24 months. These distributions will be calculated under 3 scenarios: 1) using the observed treatment-arm-pooled infection rate to-date and assuming that VE(0-24) = 25% [the null hypothesis]; 2) using the observed treatment-arm-pooled infection rate to-date and assuming VE(0-24) = 50% [the alternative hypothesis]; and 3) using the observed by-arm infection rates observed to date. Methods for performing these calculations will be specified in the SAP.

A report based on blinded data will be shared with the study OG. It will only contain projections of the treatment-arm-pooled infection total (not the arm-specific totals), and only projections under scenarios 1 and 2, since scenario 3 contains information about the observed VE to date.

The probability distribution of the Stage 1 (0-24 month) treatment-arm-pooled infection total, under design assumptions on enrollment, dropout, and infections, is shown in Table 6-5.

 Table 6-5 Distribution of Stage 1 infections (pooled over treatment arms) ignoring interim

 monitoring

True VE	Percentiles of the distribution of the number of Stage 1 infections														
(0-24)	2.5%	5%	10%	20%	25%	30%	40%	50%	60%	70%	75%	80%	90%	95%	97.5%
0%	357	362	369	377	380	383	388	393	397	403	405	409	417	424	431
50%	265	271	277	284	286	289	293	297	301	306	308	311	319	325	330

The estimated reverse cumulative distribution function (rcdf) of the pooled number of HIV infection endpoints will be shown, for each of the 3 scenarios above, for a range of endpoint counts on the x-axis. The rcdf plot will include an additional axis on the top, showing the approximate power under the proportional hazards assumption of a one-sided test with significance level 0.025 to reject H₀: $VE(0-24) \le 25\%$ assuming VE(0-24) = 50% throughout the trial, for the range of endpoint counts on the bottom x-axis. While the rcdf of the pooled number of endpoints conditions on the observed data to date, the power approximation follows an analytical formula (calculated by solving equation (1) in (114)) and disregards observed data to date to maintain trial integrity. Rcdfs will also be used to summarize the distribution of the number of HIV infection endpoints by arm.

In addition, information on use of antiretroviral drugs that could affect accrual of endpoint infections will be provided to the DSMB as available. If the HIV incidence estimates are below projected despite good retention and adherence, the DSMB may elect to engage with the protocol team and OG as to what corrective actions can be undertaken, including expanding enrollment, and using specific demographic or behavioral risk factors to enroll higher risk participants or those coming from high epidemic communities.

If the DSMB does recommend termination and the trial is stopped, then the final analysis will be performed and the results made public.

If at any time operational futility guidelines are met and yet it appears that value exists in continuing the trial, the statisticians will provide the DSMB with additional information, as appropriate, for use in their consideration of whether to recommend trial termination.

6.5.6 Operational analysis near the end of enrollment to decide whether to consider expanding enrollment

As mentioned above, the HVTN 702 OGC will receive the results of the components of the operational futility analysis that are based on blinded data. The committee will also be provided additional information at the time of a special DSMB meeting scheduled to take place approximately 3 months before the completion of enrollment—based on ongoing projections of time until full enrollment by study statisticians. For this meeting, study statisticians will prepare a report that includes the calculations typically in an operational futility analysis, along with additional guidance as to whether the HIV incidence – pooled over treatment arms—is "too low" or "acceptable" to sufficiently power the study. (The details of this guidance will be described in the study SAP.) The report will be shared both with the DSMB and with the study OG. The OG will then have the opportunity to decide whether, if incidence is lower than anticipated but not so low that operational futility is declared, to expand enrollment beyond the originally planned 5400, in order to maintain the ability of the study to meet the study's primary objectives. The meeting will be timed before but near to the end of enrollment, to allow a potential decision to expand enrollment to occur before the enrollment apparatus is scaled down, while also allowing the decision to be made on the maximal amount of primary endpoint infections. The OG may also be presented information on the degrees of enrollment expansion that would be required in order to achieve treatment arm-pooled infection totals corresponding to various levels of power to reject the primary null hypothesis if VE(0-24) =50%, approximated under the proportional hazards assumption.

6.5.7 Performance standards for quality of trial conduct

The protocol team and study investigators will have performance standards regarding the quality of trial conduct in addition to the study event rate. Some of these standards will relate to achievement of targeted levels of: (i) participant enrollment into the trial; (ii) adherence to study interventions; and (iii) retention of participants. In addition to using the above guidelines for operational futility, the DSMB and the HVTN 702 leadership will monitor whether the trial is achieving at least minimally acceptable levels regarding key performance standards.

6.5.8 Roles of study statisticians

HVTN SDMC statisticians will be "blinded" or "unblinded". During protocol development and after primary follow-up is completed, there will be no distinction between the roles; both types of statisticians will be responsible for designing and analyzing the study. During the primary follow-up period, however, only the unblinded statisticians will see interim data broken down by treatment arm. Their role will be to conduct the interim monitoring and to produce and present reports on accruing data to the study DSMB. During the primary follow-up period, blinded statisticians will see only the interim data pooled across treatment arms. This way, blinded statisticians can assist protocol leadership in

making decisions about modifications to the protocol without being influenced by interim efficacy results.

6.5.9 Power for secondary VE analysis

Secondary Objective 2 evaluates vaccine efficacy against infections diagnosed between the Month 6.5 and Month 24 visits in the per-protocol cohort. Unconditional power to address this objective is summarized in Table 6-6. For example, there is 77% power to detect VE(6.5-24) $\geq 50\%$ (versus the null of H0: VE(6.5-24) $\leq 25\%$) assuming a 10% probability that a participant misses a vaccination and is therefore not included in the per-protocol cohort.

Table 6-6 Power to detect different levels of VE(6.5-24) based on a sample size of n = 2700 per group.

True Average VE(6.5-24)	Power to reject null: VE(6.5-24) ≤ 25%				
30%	6%				
40%	31%				
50%	75%				
60%	97%				
70%	100%				
80%	100%				

Under Secondary Objective 5, vaccine efficacy will be assessed by various demographic characteristics, including gender. Given that the trial will enroll more women than men, and that HIV incidence is expected to be lower in men than in women, calculations were performed to assess the precision with which vaccine efficacy can be assessed among men. Table 6-7 describes the precision with which VE(0-24) can be estimated among men, assuming VE(0-24) = 50% and under different assumed HIV incidence rates among men. Importantly, these confidence intervals rule out VE(0-24) \leq 0%, as long as HIV incidence among men is 2.0% or more annually and 30% men are enrolled, and as long as HIV incidence among men is 1.5% or more annually, if 35% men are enrolled.

Table 6-7 Expected confidence interval around VE(0-24) = 50% among men, assuming 30% or 35% men, under different assumed HIV incidence rates among men, for a trial with n = 2700 per group

Fraction of Men in study (%)	Assumed Infection Rate for Men (% per year)	Expected Number of Infections (Men)	95% CI for VE (men)
30	1.0	22	(-0.213, 0.794)
30	1.5	34	(-0.02, 0.755)
30	2.0	45	(0.071, 0.731)
35	1.0	26	(-0.13, 0.779)
35	1.5	39	(0.027, 0.743)
35	2.0	53	(0.115, 0.718)

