7.2 Secondary Endpoints

Secondary Endpoint 1 (MITT Cohort): Durability of VE

HIV-1 infection diagnosed after enrollment through 36 months post enrollment

Secondary Endpoint 2 (Week 26 At-Risk Cohort): Week 26+ VE

HIV-1 infection diagnosed after Month 6.5 through 24 months post enrollment

Secondary Endpoint 3 (Immunogenicity Cohort): Immunogenicity

Immune responses at Month 6.5 (Week 26 visit) from assays based on the HVTN Laboratory Assay Algorithm such as vaccine-specific binding antibodies and T cell responses. The primary time-point for immunogenicity assessment is the Week 26/Month 6.5 visit, 2 weeks after the Month 6 vaccination. Immunogenicity assessments will also be performed at the Month 0, 12.5, 18, 18.5, and 24 visits (the ‘immunogenicity time-points’ for measuring immune responses; see protocol Appendix F).

Secondary Endpoint 4 (Immunogenicity Cohort): Correlates of Risk

Immune responses from assays based on the HVTN Laboratory Assay Algorithm (available at <https://atlas.scharp.org/>) and/or more assays down-selected from a larger pool of pilot studies, in HIV-1-infected vaccine cases and HIV-1-uninfected vaccine controls.

Secondary Endpoint 5 (MITT Cohort): VE by demographics, including sex at birth

HIV-1 infection diagnosed after enrollment through Month 24, and through Month 36 if Stage 2 occurs, by demographic characteristics including sex at birth

Secondary Endpoint 6 (MITT Cohort): VE by HIV genotype

HIV-1 infection diagnosed after enrollment through Month 24, and through Month 36 if Stage 2 occurs, and genotypic characteristics of viral sequences from HIV-1-infected participants at first evidence of HIV-1 infection, such as signature site mutations.

Full genome HIV-1 sequences will be measured from each subject in the MITT Infected Cohort. Five sequences will be measured at the EPIT (earliest post-infection time-point, based on the ‘look-back’ procedure) and 5 sequences will be measured at a later visit selected to be between 3 and 6 months after the EPIT.

Secondary Endpoint 7 (MITT Infected Cohort): Sieve analysis

Viral sequences from HIV-1-infected participants at the EPIT

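### Protocol 6.5.9 quotes 77% power for VE(6.5-24) = 50%, but Table 6-6, which it cites, gives 75%; recomputation supports the table

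*Protocol*

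**What the plan says.** Protocol 6.5.9 covers Secondary Objective 2, efficacy against infections diagnosed between Month 6.5 and Month 24, and places it in the per-protocol cohort. It says: "Unconditional power to address this objective is summarized in Table 6-6". The next sentence begins "For example, there is 77% power to detect" a VE(6.5-24) of 50% or more against a null of 25% or less, "assuming a 10% probability that a participant misses a vaccination and is therefore not included in the per-protocol cohort".

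The caption of Table 6-6 reads: "Power to detect different levels of VE(6.5-24) based on a sample size of n = 2700 per group". Its rows for true VE of 30, 40, 50, 60, 70 and 80% give power of 6, 31, 75, 97, 100 and 100%. The table does not restate the cohort or the 10% exclusion.

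SAP 7.2 labels the endpoint "Secondary Endpoint 2 (Week 26 At-Risk Cohort): Week 26+ VE". SAP 10.5 repeats the primary efficacy analysis in that cohort and then plans a parallel one in the Per-Protocol Cohort. Neither document gives power for VE(6.5-24) in the Week 26 At-Risk Cohort.

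**The concern.** The sentence offers its figure as an example from the table, yet 77% appears nowhere in the table. Objective, true efficacy, null and sample size are the same, so at most one of the two figures can belong to the stated scenario.

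The stake is the record of what the trial was planned to detect. Secondary Objective 2 remains in the current protocol (5.2), and a reader weighing a VE(6.5-24) result would look here for the planned power. That reader finds two figures for the per-protocol cohort and none for the cohort that the SAP attaches to the endpoint.

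**Working it through.** **Inputs.** From Protocol 6.5.9: n = 2700 per group, null VE 25%, true VE 50%, 10% excluded, window Month 6.5 to Month 24. From Protocol 6.4.1, and assumed to carry over because 6.5.9 does not restate them: placebo incidence 4% per year, dropout 5% per year, VE halved in Months 0-6 (so 25%, then 50%), one-sided alpha 0.025. Infection and dropout are taken as exponential. The exclusion is taken as 10% overall and equal in both arms.

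**Expected infections with 10% excluded** (2430 per group; window start 6.5/12 = 0.5417 years, length 1.4583 years).

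- Placebo: 2430 × exp(−0.09 × 0.5417) × (0.04/0.09) × [1 − exp(−0.09 × 1.4583)] = 2430 × 0.9524 × 0.4444 × 0.1230 ≈ 126.5.
- Vaccine: the cumulative exit rate to Month 6.5 is 0.03 × 0.5 + 0.02 × 0.0417 + 0.05 × 0.5417 = 0.0429. Then 2430 × exp(−0.0429) × (0.02/0.07) × [1 − exp(−0.07 × 1.4583)] = 2430 × 0.9580 × 0.2857 × 0.0970 ≈ 64.5.

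**Power (Wald approximation).** SE = √(1/126.5 + 1/64.5) = 0.1530. Power = Φ(ln(0.75/0.50)/SE − 1.96) = Φ(0.4055/0.1530 − 1.96) = Φ(0.69) ≈ 75.5%.

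**Reproducing the table.** A simulation of 20,000 trials per scenario used three-monthly diagnosis, 10% excluded, and a Wald test of the Nelson-Aalen cumulative incidence ratio against VE = 25%.

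| True VE(6.5-24) | Table 6-6 | Simulation |
|---|---|---|
| 30% | 6% | 6.2% |
| 40% | 31% | 31.0% |
| 50% | 75% | 74.5% and 75.3% (two runs) |
| 60% | 97% | 97.6% |
| 70% | 100% | 100% |

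The match suggests that the borrowed inputs are the right ones and that the table already includes the 10% exclusion.

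**What other settings give at true VE 50%.**

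| Setting | Wald | Simulation |
|---|---|---|
| No exclusion, Month 6.5 start | 79.8% | 79.5% |
| 5% excluded, Month 6.5 start | 77.7% | 77.3% |
| 10% excluded, Month 6.0 start | 76.8% | not run |
| 10% excluded, Month 6.5 start (as stated) | 75.5% | 74.5%, 75.3% |
| 34.4% excluded (10% at each of four visits, 1 − 0.9⁴) | 61.9% | not run |

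**Week 26 At-Risk Cohort.** With no exclusion for missed vaccination, expected infections are about 140.6 and 71.7. SE = √(1/140.6 + 1/71.7) = 0.1451, and power = Φ(0.4055/0.1451 − 1.96) = Φ(0.83) ≈ 79.8%. The Schoenfeld formula, which SAP 11.3 uses for its event targets, gives 84.0% here. It gives 80.0% for the per-protocol case, well above Table 6-6, so it is not the method that matches the table.

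**The case against.** **Simulation noise.** Protocol Table 6-3 is described as simulation-based, and Tables 6-2 and 6-3 give 90% and 91% for one and the same scenario. The number of runs is not stated. If it were 1,000 (an assumption), the standard error of the difference between two independent runs near 75% would be √(2 × 0.75 × 0.25/1000) ≈ 1.9 points. The two figures could then come from separate runs of one correct program. This stands as a possible origin and would make the mismatch an editing slip. It does not justify presenting as an example from a table a figure that the table contradicts.

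**Different inputs.** The sentence and the table might rest on different exclusion rates. If the table assumed no exclusion, it would show about 80%, not 75%. A reader might conclude that 77% implies an exclusion of only 5 to 6%. The documents do not support that: a Month 6.0 start with 10% excluded gives nearly the same value, so the source of 77% cannot be identified.

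**Cohort.** A reader might infer that the power was computed for the wrong cohort, because the SAP makes the Week 26 At-Risk analysis the main one and the per-protocol analysis merely supportive. Neither document ranks them. Protocol 6.1 and SAP section 3 list both cohorts for secondary efficacy analyses. Protocol 6.9.5.2 plans the per-protocol analysis with a Week 26 time origin. SAP section 3 holds the first VE(6.5-24) analysis until 30 per-protocol infections have accrued. Per-protocol power is therefore relevant, only incomplete. The gap is also conservative: the Per-Protocol Cohort is a subset of the Week 26 At-Risk Cohort, so at equal true efficacy its power is the lower of the two.

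**Relevance now.** Protocol 6.5 opens by saying that interim monitoring is complete and that it describes the original plan. That limits the point to correcting the record.

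**Conclusion.** The sentence in Protocol 6.5.9 is wrong as written. Its figure is 2 points above the table it cites, and the table is the figure that fits the stated scenario (75.5% by the Wald approximation, 74.5 to 75.3% by simulation). This rests on carrying the incidence, dropout, early-efficacy and alpha inputs over from 6.4.1, which the row-by-row agreement supports.

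The cohort part is an omission, not an error. The SAP names the Week 26 At-Risk Cohort for this endpoint and analyses per-protocol alongside it, and only the per-protocol power is given. The other is about 4 points higher by the Wald approximation (79.8% against 75.5%). That figure is rough: it depends on the method, and it assumes that everyone still in follow-up and uninfected at Month 6.5 enters the cohort, whereas membership requires HIV-negative status at or after the Week 26 visit.

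This is a minor correction.

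**What to change.** In Protocol 6.5.9, replace 77% with 75%, and label Table 6-6 as the per-protocol cohort with 10% excluded for a missed vaccination. If the sponsor prefers to keep 77%, the inputs behind it must be stated.

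Add one sentence giving VE(6.5-24) power for the Week 26 At-Risk Cohort, computed with the same simulation as Table 6-6. The approximate 80% above is a check on that figure and should not be copied in. Name both cohorts as SAP 7.2 and 10.5 do, without calling either one main or supportive.

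The cost is one figure, one label, one sentence and one further run of a simulation the sponsor already has. The quoted per-protocol power falls by 2 points. Conduct, sample size and the primary analysis do not change.
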